## **17. Protocol Procedures, Methods, and Duration - in nontechnical, lay language**

- a. Describe the procedures for all aspects of your protocol. Tell us what you are doing.  
The overall goal of this 5-year Mentored Research Scientist Development K01-Award is to support [name], MPH become an independent investigator in the field of HIV prevention. The proposed project seeks to address the HIV crisis in Alabama, where rates of undiagnosed HIV in black young men who have sex with men (YMSM, 18-29 years) exceed 20%. This project will adapt and test a behavioral intervention to promote HIV rapid testing in the community, deliver culturally appropriate prevention education, offer sociostructural supports, and refer eligible participants for pre-exposure prophylaxis (PrEP). Three specific aims are proposed as part of the pilot study.

Aim 1 is to elucidate experiences, beliefs, and predictors related to delivery and utilization of HIV testing and prevention services by black YMSM using qualitative research methods to inform the adaptation of the Brothers Saving Brothers (BSB) intervention. Aim 2 is to adapt the BSB intervention to include two HIV prevention tools (rapid testing and PrEP), to address structural barriers, and to be acceptable to black YMSM in Alabama. Aim 3 is to conduct a hybrid type 1 effectiveness-implementation pilot study of the adapted intervention

[figure not shown]
### **PROCEDURES FOR AIM 1**

I intend to conduct focus groups and interview with racial gender and sexual minorities. My prompts will focus on elucidating specific ways to adapt BSB to navigate the sociocultural (southern) environment of these youth. In-depth interviews with community based organization (CBO) staff will be conducted. Topics will include: 1) Views on how youth-friendly their services are, 2) Thoughts on how minority-friendly their services are, 3) What language they use to explain PrEP and prevention to clients, 4) Opinions on how to increase rates of prevention services by minority youth and YMSM, and 5) Sociostructural support services available.

## PROCEDURES FOR AIM 2

After the conclusion of Aim 1, I will use the 4-step intervention mapping model (for HIV) to adapt BSB (see Figure 1). I anticipate having to adapt the intervention 2-4 times. Each version of the adapted intervention will be demonstrated to YMSM and CBO staff using face-to-face roleplays. If I find traits of a prior version were better received, I will revert to those in the next cycle. After the intervention is finalized, select CBO staff will be trained in the intervention. I will conduct this face-to-face training to bring CBO staff to solid fidelity.

Figure 1. Intervention Mapping Conceptual Framework for BSB Adaptation

## PROCEDURES FOR AIM 3

After Aim 2 is concluded, and I have a testable version of the BSB intervention, I will work with CBO staff recruit and enroll black YMSM. Potential study participants will directly enter data into an iPad screener (iSurvey). The device will determine eligibility. Inclusion criteria include age, identifying as Black, English speaking, resident of Alabama, being sexually active with men, identifying as male, and has not taken an HIV test in the prior 6-months. If eligible, the participant will be asked to provide informed consent. The system will then randomize participants to BSB or control. Block randomization will ensure a balance across intervention and control groups. See table below for characteristics of both. We will collect data on if the participant was willing to take an HIV test, if the participant started PrEP within 6-months, and if the participant re-tested for HIV within 6-months. We will collect self-report data on the participant's behaviors related to HIV prevention and personal characteristics from the participant before the intervention, after it, 3-months later, and 6-months later. These questionnaires have not yet been developed and are scheduled to be developed in Year 3 on the grant (2021-2022). Once developed, these questionnaires will be shared with the UAB IRB via amendment for approval. All interviews and intervention activities will be conducted in a private space. All HIV test results will be shared in a private space. Regardless of test reactivity, the way test results are shared will be standard, so that an onlooker cannot discern a test result by how the study participant was "treated." For those with a reactive test, the outreach worker will actively navigate the study participant to care for a confirmatory test. If the results show that the participant is positive for HIV, the study staff will tell the participant the results. The study staff will be required to give the participant's name to the Alabama Department of Public Health, because this is the law. If the participant is entered and completes the entire study, the participant will be in the study for 6 months. Selma AIR staff will be part of this Aim and will not be recruited until 2021-2022. At that time, an amendment will be submitted to the OIRB via PRAF indicating additional personnel.

### BSB Intervention Specification and Unique Features

Characteristic	Standard Street Outreach	Brothers Saving Brothers (BSB)
Presentation	Presents as expert providing information and services	Communicates respect for clients as experts on their own behavior and emphasizes personal choice and responsibility
Assessment	Focuses on brief risk assessment	Focuses on assessment of readiness to learn HIV status in addition to brief risk assessment
Education	Focuses on providing standardized HIV education	Focuses on exploring ambivalence about learning HIV status with tailored education as needed
Support for Self-Efficacy	No specific component	Verbally affirms specific strengths to boost confidence for behavior change

Overall Communication	Training involves presenting information in a non-judgmental, respectful manner	Training involves specific client-centered micro-skills and strategies to elicit and reinforce motivational statements
-----------------------	---	--

b. What is the probable length of time required for the entire protocol (i.e., recruitment through data analysis to study closure)? 4 years

c. What is the total amount of time each participant will be involved? Maximum 4 years (staff). If CBO staff are engaged at the onset of the study and are still available at the conclusion, they could be participatory for the full 4-years. Black YMSM who participant in focus groups or in-depth interviews will be engaged for 1 day. Black YMSM who enroll in the effectiveness-implementation study will be active for 6 months.

d. If different phases are involved, what is the duration of each phase in which the participants will be involved? If no phases are involved, enter "None." None

e. List the procedures, the length of time the procedure takes, the total # of times the procedure is performed, and indicate whether each is performed solely for research or would already be performed for treatment or diagnostic purposes (routine care) for the population.  
*-Insert additional table rows as needed.*  
*-If procedure is sometimes research and sometimes routine care, include on separate lines with number of times as each.*

Procedure	Length of Time Required of Participants	Total # of Times the Procedure is Performed	Research (Res) —OR— Routine Care
Focus Group	1 hour	1	 Res  Routine
Interview	1 hour	1	 Res  Routine
Intervention adaptation	2 hours	1-2	 Res  Routine
Intervention	1 hour	1	 Res  Routine
HIV Test	10 minutes	1	 Res  Routine
PrEP Initiation	30 minutes	1	 Res  Routine
HIV Retesting	10 minutes	1	 Res  Routine
Survey	15 minutes	4	 Res  Routine

f. Will an interview script or questionnaire be used?  Yes  No  
If Yes, attach a copy.

g. Will participants incur any costs as a result of their participation?  Yes  No  
If Yes, describe the reason for and amount of each foreseeable cost. \_\_\_\_\_

h. Will participants be compensated?  Yes  No  
If Yes, complete i-v.

- Type: (e.g., cash, check, gift card, merchandise): Direct Deposit, Cash, or Gift Card
- Amount or Value: CBO staff will be eligible for incentives of \$35 for participation in an in-depth interview. Young adults (YMSM participants) will be eligible for incentives of \$35 for participation in a focus group, in-depth interview, or study questionnaire.
- Method (e.g., mail, at visit): Visit
- Timing of Payments: (e.g., every visit, each month): At each data collection point
- Maximum Amount of Compensation per Participant: \$175

## 18. Benefits

Describe the potential benefits of the research. Primary benfit of this study, if successful, is the development of a low-cost method to promote HIV testing and PrEP uptake in this community.

## 19. Risks - in nontechnical, lay language

a. List the known risks for participants as a result of participation in the research. This should not include the minimal risk of loss of confidentiality. However, it should include any physical, psychological, social, economic, and/or legal risks. If there is a greater than minimal risk of loss of confidentiality describe why this is so. Do not list risks associated with the standard-of-care procedures.

*NOTE: Risks included here should be included in the consent form or information sheet, as applicable.*

**Minimal risks may include the possibility of temporary increased stress for participants during the intervention interactions. If psychological distress occurs, participants will be informed that they may stop the study at any time if they feel uncomfortable. Staff in-depth interviews, however, will not focus on sensitive or personal aspects of their own behaviors, so for the staff many of these risks are of very low probability.**

b. Estimate the frequency, severity, and reversibility of each risk listed. **Psychological stress and discomfort, minutes – minor – quickly reversed.**

c. Is this a therapeutic study or intervention?

Yes  No

If Yes, complete i.-iii.

i. Describe the standard of care in the setting where the research will be conducted: **There is not a systematic way in which to deliver community-based HIV testing; thus standard of care is variable from person to person.**

ii. Describe any other alternative treatments or interventions: **None**

iii. Describe any withholding of, delay in, or washout period for standard of care or alternative treatment that participants may be currently using: **None**

d. Do you foresee that participants might need additional medical or psychological resources as a result of the research procedures/interventions?

Yes  No

If Yes, describe the provisions that have been made to make these resources available. \_\_\_\_\_

e. Do the benefits or knowledge to be gained outweigh the risks to participants?

Yes  No

If No, provide justification for performing the research: \_\_\_\_\_

## 20. Precautions/Minimization of Risks

a. Describe precautions that will be taken to avoid risks and the means for monitoring to detect risks. **My mentoring team and I will have taken additional measures to protect participants from study-related risks, including creating a Data and Safety Monitoring Board (DSMB), to review study procedures and any adverse events. Considering reviewer feedback around protections of human subjects and the vulnerability of YMSM of color in the Deep South (Alabama), my mentors and I determined that a DSMB is both warranted and prudent to convene in an effort to protect study participants. The DSMB will address adverse events (AE) and severe adverse events (SAE). Members of the DSMB have not been identified yet; however, in the proposal to the NIH, potential DSMB members were described as “Members of this DSMB will have experience with conducting research with young minority populations that are at high-risk for contracting HIV, HIV-infected persons, including those who are new to HIV care, and young gender and sexual minorities in high-stigma settings.” Potential members of the DSMB will be experienced in the ethics of conducting research with high-risk for contracting HIV populations.**

If the protocol involves drugs or devices skip Items 20.b. and 20.c. and go to Item 21. Instead include this information in the [Drug Review Sheet](#) or [Device Review Sheet](#), as applicable.

b. If hazards occur to an individual participant, describe (i) the criteria that will be used to decide whether that participant should be removed from the protocol; (ii) the procedure for removing such participants when necessary to protect their rights and welfare; and (iii) any special procedures, precautions, or follow-up that will be used to ensure the safety of other currently enrolled participants.

If an HIV test is reactive, outreach workers are trained to navigate the participant to care (for confirmatory test). Those with a reactive test will not receive the second part of aBSB. Their data collected prior to the first part of aBSB will be included in the analyses. If a participant appears to be in emotional distress, study staff will inquire as to the participant's well-being and whether they wish to stop the study visit. Participants who opt to stop the study visit, or who disclose potentially harmful information (e.g., suicidality) will be immediately referred for an assessment by a clinic social worker, psychologist, or counselor. We will enact the CBO's emergency protocol for persons who need immediate attention for escort to the local emergency department.

c. If hazards occur that might make the risks of participation outweigh the benefits for all participants, describe (i) the criteria that will be used to stop or end the entire protocol and (ii) any special procedures, precautions, or follow-up that will be used to ensure the safety of currently enrolled participants. There are no foreseeable potential hazards that would outweigh the benefits for all persons.

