## **PROTOCOL**

The purpose of this study is to adapt and test Brothers Saving Brothers, a brief two-part intervention that has been shown to increase rates of HIV testing and acceptance of prevention education in Midwest Black young men who have sex with men but has not been adapted for the South. This will be accomplished by updating it for rapid testing, pre-exposure prophylaxis education, and to include structural supports. We will pilot-test the adapted intervention to estimate intervention effects.

Community Based Organization staff will facilitate the enrollment process. Potential participants will directly enter data into a virtual screener via Qualtrics. Data will be directly uploaded and stored on a secure, encrypted server. Inclusion criteria include age, identifying as Black, English speaking, resident of Alabama, being sexually active with men, identifying as male, and has not taken an HIV test in the prior 6 months. If eligible, the participant will be asked to provide informed consent. Informed consent will include the request to access medical records related to HIV re-testing and pre-exposure prophylaxis. Limited data on rates of pre-exposure prophylaxis exist, but since this study is with high-risk for HIV young men who have sex with men, we anticipate most participants will be eligible for pre-exposure prophylaxis per guidelines. After informed consent is collected, pre-study survey data will be self-reported. The system will then randomize participants to Kings or the standard control condition in a 2:1 allocation. Participants will be followed by 6-months post-enrollment.

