## **DATA COLLECTION**

All data collection will occur via secure digital link to online surveys that will be linked by unique, anonymized participant identification numbers. Data collection, via this process will occur in the (1) screener, (2) pre-randomization, pre-intervention or control data collection, (3) post- data

collection, (4) 3 months post-data collection, and (5) 6 months post data collection, Please see the trial's schema below.

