## STATISTICAL ANALYSIS PLAN

Descriptive statistics will be used to identify the characteristics of the sample. Baseline differences between the intervention group and control group will be examined using student's t tests (for continuous variables) or chi-square tests (for categorical variables). Second, the feasibility / acceptability / satisfaction will be evaluation through multiple indicators, with focus on the simple question, "I like this app."

Preliminary efficacy of the intervention will be assessed using both bivariate statistics (e.g., t test, chi-square test, and fisher exact test) and multivariate statistics adjusting for demographic factors and baseline differences. To examine the preliminary effect of the intervention, we compared changes over time in HIV knowledge, pre-exposure prophylaxis knowledge, internalized homophobia, everyday discrimination, and medical mistrust within each group, as well as the increase from baseline to 6-month between the two groups. We also will assess the differences in willingness to take HIV test, self-reported HIV testing rates, and interest in learning more about pre-exposure prophylaxis and pre-exposure prophylaxis consultation with prescription between the two groups using Chi-square and Fisher's exact test. The effect of the intervention will be further examined using a generalized estimating equation controlling for potential confounders including education, income and social support. All statistical analyses will be performed using the SAS 9.4 statistical software package.

Institutional Review Board  
**Protocol Oversight Review Form**Date Submitted to IRB: August 15, 2018Title of Project: Adapting and Pilot Testing a Behavioral Intervention to Incorporate Advances in HIV Prevention for Black Young MSM in AlabamaName of Principal Investigator: [name]

Signature of Principal Investigator: \_\_\_\_\_

School: Public HealthDepartment: Health Care Organization and PolicyDivision: NA

Review Process (as determined by Department Chair):

Departmental Review  
 Divisional Review (Division Director or Designate)  
 Center or Departmental Protocol Review Committee Review  
 Project Review Panel (PRP)—Appointed by the Department Chairman or Division Director (PRP report attached)

[figure not shown]
---

I have reviewed the proposed research and concluded that the following apply:

- The research is scientifically valid and is likely to answer the scientific question;

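### The IRB form implies that men with a reactive HIV test contribute only pre-intervention data, which would drop men from the testing outcome because they tested; control handling is unstated and the SAP is silent

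*Combined protocol and SAP*

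**What the plan says.** Item 20.b of the IRB form asks, among other things, for "the criteria that will be used to decide whether that participant should be removed from the protocol". The answer opens with what happens after a reactive test (navigation to confirmatory testing) and names no arm. It then says that such participants do not get the second part of aBSB, the adapted intervention that the protocol calls Kings, and adds: "Their data collected prior to the first part of aBSB will be included in the analyses".

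Other sections plan data collection with no exception for reactive results:

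- IRB form, item 17.a, Procedures for Aim 3: "We will collect data on if the participant was willing to take an HIV test". Self-report data are to be taken "from the participant before the intervention, after it, 3-months later, and 6-months later".
- Protocol, Data Collection: a post-session survey and surveys at 3 and 6 months, for all participants.

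The Statistical Analysis Plan makes testing a between-arm outcome: "We also will assess the differences in willingness to take HIV test, self-reported HIV testing rates". It defines no analysis set, does not say that participants are analysed as randomised, and gives no rule for reactive tests. It neither repeats nor withdraws the sentence in item 20.b.

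**The concern.** Naming a cut-off before the first part of the intervention, in reply to a question about removal, implies that data after the cut-off are not used. Test acceptance and every follow-up survey come after it.

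A reactive result requires that the man took the test, so each man affected is a success on test willingness, a behaviour the intervention is meant to change. Leaving these men out is a selection made after randomisation and determined by the outcome.

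The rule is also written in terms of aBSB. The control condition, standard street outreach, has no first part of aBSB, so a reader cannot tell what happens to a control man with a reactive test. If the rule is applied to Kings alone, the comparison is biased against Kings. If it is applied to both arms, both testing rates are too low. An analyst could follow either version or neither, and the reported rates would differ.

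**Working it through.** **Order of events.** Item 20.b withholds the second part after a reactive test, so the test comes before part two. The data cut-off comes before part one. Test acceptance therefore falls after the cut-off, as do the post, 3-month and 6-month surveys.

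**Inputs from the documents.** Enrolment was 59 (Sample Size). The protocol says the system will "randomize participants to Kings or the standard control condition in a 2:1 allocation", which gives about 39 Kings and 20 control (59 × 2/3 = 39.3; 59/3 = 19.7). The documents state no effect size, alpha or power, so there is no figure of the plan's own to reproduce.

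**Assumptions.** Uptake *p* is 60% in Kings and 40% in control, a true risk difference (RD) of 20 points. The reactive share *r* of accepted tests is 5%, 10% or 20%, the same in both arms. The abstract's figure for undiagnosed HIV (above 20%) has no stated denominator and is not used as *r*.

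**Formula.** If reactive testers are dropped, a fraction *p·r* leaves both numerator and denominator:

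observed uptake = *p*(1 − *r*) / (1 − *p·r*)

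For Kings at *r* = 0.10: 0.6 × 0.9 / (1 − 0.06) = 0.54 / 0.94 = 0.5745. For control: 0.4 × 0.9 / (1 − 0.04) = 0.36 / 0.96 = 0.3750.

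| | r = 5% | r = 10% | r = 20% |
|---|---|---|---|
| Kings uptake after dropping (true 60%) | 58.8% | 57.4% | 54.5% |
| Control uptake after dropping (true 40%) | 38.8% | 37.5% | 34.8% |
| RD, Kings only dropped (points) | 18.8 | 17.4 | 14.5 |
| RD, both arms dropped (points) | 20.0 | 19.9 | 19.8 |
| Expected Kings men lost (39 × 0.6 × *r*) | 1.2 | 2.3 | 4.7 |
| Expected control men lost (20 × 0.4 × *r*) | 0.4 | 0.8 | 1.6 |

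**If the lost outcome is coded as not tested.** Kings uptake becomes *p*(1 − *r*) = 57%, 54% or 48%. With the rule in Kings only, the RD is 17, 14 or 8 points.

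**No true effect.** At 60% uptake in both arms, dropping Kings men only produces a false difference of −1.2, −2.6 or −5.5 points.

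**The direction can reverse.** At 80% v 50% and *r* = 20%, dropping both arms gives 0.64/0.84 − 0.40/0.90 = 0.7619 − 0.4444 = 31.7 points against a true 30.0, slightly in favour of Kings.

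**Scale.** The 95% half-width of the RD at 60% v 40% is 1.96 × √(0.24/39 + 0.24/20) = 0.264, about 26 points.

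**Allocation.** Item 14.b of the IRB form gives 30 v 30, not 2:1. Observed uptake and the RDs above do not depend on the ratio. With 30 in Kings, the expected loss there is 0.9, 1.8 or 3.6 men.

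**The case against.** The case for leaving the plan alone has four parts.

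1. **The exclusion is inferred.** The sentence states what is included and says nothing of later data. It may be meant to reassure that missing part two does not remove a man from the dataset, or it may be a slip for a cut-off before part two. This stands as a limit: exclusion is an implication and not an explicit rule. But a cut-off before part two would still leave out the 3- and 6-month surveys, and uncertainty about the meaning is itself a reason to correct it.

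2. **The form is old.** It carries an August 2018 submission date and describes features later replaced: the iSurvey screener and 30 v 30 arms, where the protocol has Qualtrics and 2:1. The SAP contains no such rule. This also stands in part, since the documents do not show whether the rule reached the Kings analysis. But the form is part of the combined document, nothing withdraws the sentence, and the SAP puts no other rule in its place.

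3. **The effect is small and its size assumed.** This is true. The shift in the RD is at most 5.5 points in the main scenario when men are dropped, and nearly nil if both arms are treated alike. The pilot is explicitly unpowered. Yet estimating intervention effects is its stated purpose, and wide intervals do not excuse an avoidable bias.

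4. **Enrolment is finished, and later surveys from reactive men may not exist.** If they were not collected, they cannot be recovered. Test acceptance does not depend on them, because a reactive result already shows that the man took the test. The fix asks only for surveys that were completed.

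**Conclusion.** The concern holds. On its natural reading, item 20.b excludes men after randomisation because of an outcome that the SAP compares between arms. It conflicts with the collection schedule in item 17.a and in the protocol's Data Collection section, and the SAP does not settle the matter.

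Under the stated assumptions, dropping these men from Kings alone costs 1.2 to 5.5 points of a true 20-point difference, and 3 to 12 points if they are coded as untested. Dropping them from both arms barely moves the difference in the main scenario but understates each arm's rate by 1.2 to 5.5 points. Size depends on uptake and reactive share, which the documents do not give. Direction depends on whether one arm or both are affected, which they do not say.

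This should be fixed. Confidence is medium, because the exclusion is implied and the form predates the current protocol.

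**What to change.** Replace the data sentence in item 20.b, and state in the SAP:

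> All randomised participants are analysed in their assigned arm. Anyone who accepts the HIV test counts as tested whatever the result, in both arms. All completed post, 3-month and 6-month surveys are analysed.

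Report the number of participants with a reactive test by arm. Define separately, and identically in both arms, how they are handled for the PrEP and re-testing outcomes. If the analysis has already been done, state which rule was applied.

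The cost is one SAP paragraph and one replaced sentence. No new data are needed, because test willingness and the later surveys are already planned. Who receives the second part of the session is not affected.
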